Carolinan HealthCare System

Transarterial embolization and microwave ablation combination
therapy in early-stage hepatocellular carcinoma: A randomized trial

Project Lead: [name]

Principal Investigator: [name], PhD, FACS, FRCSC

Coinvestigators: [name], FACS; [name], FACS; and [name], MD

Hepatopancreaticobiliary Division, Department of Surgery,
Carolinan Medical Center
Charlotte, North Carolina 28203

Summary

This single-center, prospective RCT is designed to compare the outcomes and clinicopathologic results of blunt transarterial embolization (TAE) and microwave ablation (MWA) combination therapy with MWA monotherapy for the treatment of early (stages 0 and A) hepatocellular carcinoma (HCC). The primary aim of this study is to test the following hypothesis: 2-year intrahepatic disease-free survival does not differ between patients receiving the experimental therapy (MWA + TAE) and patients receiving the standard therapy (MWA alone) as treatment for early stage HCC. Secondary aims are: 1) to determine the clinical feasibility of TAE + MWA in HCC patients with a small tumor burden using patient demographics and disease characteristic data and 2) to determine the effect of TAE on radiographic tumor characteristics in this patient cohort.

Principal Investigators

[name], PhD, FACS, FRCSC

Co-Investigators

[name], FACS

[name], FACS

[name]

Main Center

Levine Cancer Institute, Carolinas Medical Center, Charlotte, NC 28203

Sponsor

Carolinas Healthcare Systems

Table of Contents

BACKGROUND.....	44
STUDY DESIGN	66
Objective.....	66
Methods.....	77
Patient Eligibility and Allocation	77
Sample Size	99
Surgery	10
Data Collection.....	1111
Statistical Analysis.....	1313
ETHICAL AND SAFETY CONSIDERATIONS	1414
Protection of Patients	1414
Protection of health care providers.....	1414
Protection of environment	1515
REFERENCES.....	1717
APPENDIX I: BCLC Classification of HCC	1919
APPENDIX II. THE CLAVIEN-DINDO CLASSIFICATION OF SURGICAL COMPLICATIONS.....	2020
APPENDIX III: LIVER IMAGING REPORTING AND DATA SYSTEM (LI-RADS) CRITERIA FOR HCC	2121
APPENDIX IV: DIAGNOSTIC WORK-UP/PATHWAY	2222
APPENDIX V: PERIOPERATIVE CARE PATHWAY FOR HCC	2323
APPENDIX VI: PHARMACOKINETIC PARAMETERS OF CHEMOTHERAPEUTIC AGENTS	2424

BACKGROUND

According to the GLOBOCAN 2008 estimates, over 749,000 new cases of liver cancer are diagnosed and 695,000 deaths from liver cancer occur worldwide each year¹. Hepatocellular carcinoma (HCC) accounts for 75-90% of the total liver cancer burden worldwide and most often occurs in the setting of chronic liver disease and cirrhosis². Surgical resection is the only treatment option that offers the potential of long-term survival; however, due to advanced, multifocal disease at diagnosis or lesions proximal to critical structures, fewer than 5% of patients are candidates for surgery. Overall 5-year survival following a diagnosis of HCC is <16%³.

Prognostic variables including tumor status (number and size of nodules, vascular invasion, and N1 and M1 staging), liver function (Child-Pugh's class, bilirubin, albumin, portal hypertension, ascites), and patient health (Eastern Cooperative Oncology Group (ECOG) performance status and symptomology) are used by the Barcelona-Clinic Liver Cancer (BCLC) guidelines for classification of HCC into 5 stages (0, A, B, C, and D) (Appendix I)⁴. This classification is intended to predict outcome and to enable appropriate treatment allocation for each HCC patient. Resection is recommended for patients with BCLC Stage 0 (very early) disease, which is characterized by the presence of a single tumor <2 cm in diameter without vascular invasion/satellites in patients with good health status (ECOG-0) and well-preserved liver function (Child-Pugh A class)⁴. However, resection does not address the precancerous remnant liver, especially in the setting of cirrhosis, where progressive organ decompensation and ongoing hepatocarcinogenesis often lead to recurrence. The rate of recurrence of HCC at 5 years post-surgery is 60–70%^{5,6}, and the majority of these recurrences are limited to the liver and develop in the first postsurgical year⁶. Clearly, more effective operative techniques and treatment modalities are needed to improve clinical outcomes of surgical resections for early-stage HCC.

Microwave ablation (MWA) has emerged as an accepted alternative to surgical resection for early-stage HCC. MWA delivers energy rapidly, directly, and uniformly into target tissues without the detrimental effects of tissue impedance experienced with radiofrequency ablation (RFA), which is also used often in the setting of early-stage HCC⁷. Multiple clinical trials have reported that percutaneous and operative MWA is safe and effective⁸⁻¹³, equivalent to RFA in terms of periprocedural morbidity¹⁴, and equivalent or superior to RFA in terms of local recurrence^{10,15-17} for treatment of primary and metastatic liver tumors. However, a recent retrospective outcome analysis of patients receiving RFA or MWA for early-stage HCC reports a high rate of local recurrence in routine clinical practice¹⁸, which supports published recurrence rates of 10.5–24% following MWA in early-stage HCC^{19,20}. Poorly-differentiated HCC and

pretreatment α -fetoprotein (AFP) were identified as independent predictors of local tumor progression in these patients¹⁸. Therefore, thermal ablation modalities have a proven role in the treatment of HCC, though their role in lieu of resection in early-stage HCC is currently under debate.

Blunt transarterial embolization (TAE) is currently used predominantly as a palliative therapy for unresectable HCC²¹. In recent years, the technique of combining thermal ablation techniques with TAE has aimed to increase complete tumor response rates and reduce local recurrences. Randomized²² and nonrandomized²³ trials comparing the combination treatment of TAE and RFA with RFA alone in patients with HCC lesions <3 cm in diameter show conflicting results in terms of overall survival and progression-free survival. However, previously published reports have consistently found that the combination treatment carries equivalent risk of complications and mortality compared with thermal ablation alone²⁴. Though use of MWA remains less common than RFA in this setting, recent investigations have demonstrated improved efficacy of MWA in combination with TAE for the treatment of large²⁵ and small²⁶ HCC lesions.

Despite these suggested therapeutic benefits of combined thermal ablation and embolization techniques, little is known about the prognostic effects of MWA + TAE in early-stage HCC. To our knowledge, no RCTs have compared the combination therapy (MWA + TAE) with monotherapy (MWA alone) in this selective cohort. The efficacy of MWA in combination with TAE as a prophylactic treatment to reduce recurrence in HCC patients with a small tumor burden is unknown. Moreover, the optimal protocol and timing for MWA combined with TAE as a treatment for early stage HCC has yet to be determined. For all of these reasons, RCTs are required to examine the feasibility as well as the possible therapeutic and/or survival benefits of combination MWA + TAE in selected patients with early-stage HCC.

STUDY DESIGN

Objective

This single-center, prospective RCT is designed to compare the outcomes and clinicopathologic results of blunt transarterial embolization (TAE) and microwave ablation (MWA) combination therapy with MWA monotherapy for the treatment of early (stages 0 and A) hepatocellular carcinoma (HCC). The primary aim of this study is to test the following hypothesis: 2-year intrahepatic disease-free survival does not differ between patients receiving the experimental therapy (MWA + TAE) and patients receiving the standard therapy (MWA alone) as treatment for early-stage HCC. Secondary aims are: 1) to determine the clinical feasibility of TAE + MWA in HCC patients with a small tumor burden using patient demographics and disease characteristic data and 2) to determine the effect of TAE on radiographic tumor characteristics in this patient cohort.

The primary outcome is 2-year intrahepatic disease-free survival, which is measured from time of randomization and is defined as the absence of local or regional recurrence of HCC as determined by diagnostic imaging. *Local recurrence* is defined as an enhancing lesion contiguous with the ablation zone that is present on subsequent imaging but was not present on the initial postablation scan. *Regional recurrence* is defined as hepatic recurrence that is not adjacent to the ablation site.

Secondary outcome measures include:

- Patient and disease characteristics (Table 1)
- 1-year, 2-year, 3-year, and 5-year overall survival;
- 1-year, 3-year, and 5-year intrahepatic disease-free survival;
- Number of TAE procedures required (for multilobar lesions or repeat effect)
- Toxicity induced by TAE and or MWA using the latest published full version of Common Terminology Criteria for Adverse Events ([CTCAE v5.0](#) is slated for release in October 2015; [CTCAE v4.0](#) is available currently)
- 1-month and 3-month postoperative morbidity using the Clavien-Dindo Classification of Surgical Complications²⁷ (Appendix II);
- 1-month and 6-month postoperative mortality

- Ablation characteristics including tumor location by hepatic segment, proximity to a portal pedicle, number of applications, power settings, and ablation duration (per application and per tumor)
- Radiologic tumor observations applied to the Liver Imaging Reporting and Data System (LI-RADS) criteria at 4-6 weeks post-ablation, every 3 months for the first 2 years, and every 6 months thereafter
- AFP levels: baseline (preoperative/at diagnosis), 4-6 weeks post-ablation and TAE, every 3 months for the first 2 years, and every 6 months thereafter
- Return of bowel function (days), subdivided in: time until first stool, introduction of liquid or solid diet;
- Length of hospital stay (days);
- Length of ICU stay (days);
- 30- and 90-day readmission rates;
- Return to normal activity (days), i.e., return to full activity, work, or sport;
- Preoperative (baseline), 6-month and 1-year postoperative quality of life (QOL), using the Standard form 36 (SF-36 v 1.0) customized for HCC
- For those patients who go on to resection:
 - Duration of resection operation (minutes), defined as incision to dressing time;
 - Correspondence between pre-randomization clinical/radiologic/laboratory evaluation and intraoperative findings

Methods

Patient Eligibility and Allocation

Eligible patients will be identified in collaboration with the Levine Cancer Institute (LCI) at Carolinas Medical Center (CMC). The Institute functions as a series of integrated cancer programs distributing high-quality cancer care system-wide and houses nine cancer clinics, infusion therapy, palliative care and clinical trials, and state-of-the-art technology to connect member institutions across the Carolinas and worldwide. CMC is a high-volume center for the treatment of hepatocellular carcinoma and is one of only a few hospitals across the nation to utilize minimally invasive microwave ablative therapies to treat liver cancer. Approximately 60 MWA and several hundred TAE procedures are performed annually

with either an open, laparoscopic, or robot-assisted laparoscopic approach. **The expected enrollment rate is 2 patients/month.**

Patients diagnosed with primary HCC classified as stage 0 (very early) or stage A (early) will be considered for inclusion in this study. Tumors will be staged preoperatively with computed tomography (CT) and/or magnetic resonance imaging (MRI). Laparoscopic ultrasound will be performed intraoperatively.

Eligible patients will meet the following inclusion criteria:

- Male or female patients aged ≥ 18 and ≤ 75 years
- Primary diagnosis of HCC according to the guidelines published by the American Association for the Study of Liver Diseases (AASLD)²⁸ and the diagnostic criteria used by the European Association for the Study of the Liver (EASL)²⁹:
 - Two imaging techniques showing typical features of HCC; or
 - Cytologic/histologic diagnosis of HCC; or
 - Radiographic classification as LIRAD 5 (Appendix III), regardless of AFP level.
- HCC classification of stage 0 (very early) or stage A (early) according to BCLC staging system criteria (Appendix I):
 - Solitary HCC lesion < 3 cm in diameter
 - ≤ 3 HCC lesions, each ≤ 3.0 cm in diameter
- Total bilirubin level, with or without portal hypertension, less than or equal to 3.0.
- Adequate clinical condition to undergo laparoscopic or robot-assisted laparoscopic TAE and/or MWA as treatment for HCC
- Willing and able to give informed consent

Patients meeting the inclusion criteria will be subjected also to the following exclusion criteria:

- Radiologic (CT or MRI) evidence of invasion into major portal/hepatic venous branches and no extrahepatic metastases (LR-5V or LR-M radiologic classifications)
- Evidence of residual disease at first post-MWA CT examination
- Body Mass Index (BMI) > 35
- Previous history of hepatic resections
- Severe renal dysfunction (creatinine clearance of < 40 mL/min)

- Pregnant or nursing women

According to a computer-generated variable size blocked randomization method, eligible patients will be allocated on a 1:1 basis to receive the experimental therapy (MWA + TAE) and standard therapy (MWA alone), respectively. The nature of the treatments and their possible adverse effects preclude the use of double-blind and double dummy techniques. In patients randomized to receive the experimental therapy, TAE treatments will be initiated within one week of randomization, then followed by MWA within 4 to 6 weeks after reviewing radiological scans from TAE. MWA will be performed 4 to 6 weeks following randomization in MWA standard therapy groups. Treatment may be discontinued if any exclusion criteria develop in the patient or at the patient's request.

Sample Size

Power calculations are based upon expected 2-year survival rates. The main endpoint is 2-year intrahepatic disease-free survival, measured from the time of randomization which is measured from time of randomization and is defined as the absence of local or regional recurrence of HCC as determined by diagnostic imaging. Considering an estimated 80% and 90% intrahepatic disease-free survival at 2 years of follow-up for patients receiving MWA alone and MWA + TAE combination therapy, respectively, a sample size of 92 patients is required to detect a clinically meaningful 10% absolute difference in 2-year peritoneal disease-free survival with MWA + TAE with a minimum of 95% power and a 2-sided $\alpha = .05$. To account for a 5–10% withdrawal rate (following intraoperative detection of vascular invasion or extrahepatic metastasis, etc.), a sample size of 100 patients is required (50 patients per arm). If the rate of patient enrollment is suboptimal, a covariate adaptive randomization method will be used to allocate patients in a 2:1 ratio to receive experimental therapy (MWA + TAE) and standard therapy (MWA alone), respectively, which would result in an overall sample size of 83 patients.

Clinical Procedures

Preprocedural Strategy

Before randomization, patients will be assessed with either MRI or triphasic CT imaging and evaluated for baseline liver function, hematology, coagulation studies, and serum AFP. Liver function and underlying disease burden will be staged with the Child-Turcotte-Pugh criteria and the BCLC classification, respectively (Appendix IA and B). Radiologic findings will be reported according to the LI-RADS criteria. Patient demographics, histologic analysis, and assessment of portal vein hypertension and its sequelae will also be recorded. Patients will receive pre-operative counseling.

Carolinas Medical Center follows already established Enhanced Recovery After Surgery (ERAS) SMART™ protocol for the pre-, intra-, and postoperative care of patients undergoing certain procedures in the hepatopancreatobiliary Division. Division-specific standard guidelines will be applied to the care of patients included in this study.

Procedural Strategy

For MWA and TAE procedures, patients will be given general anesthesia. In patients randomized to receive the experimental therapy, TAE treatments will be initiated within one week of randomization, then followed by MWA within 4 to 6 weeks after reviewing radiological scans from TAE. MWA will be performed 4 to 6 weeks following randomization in standard MWA therapy groups. Treatment may be discontinued if any exclusion criteria develop in the patient or at the patient's request.

For TAE procedures, moderate/procedural or general anesthesia will be induced. A selective 5-F catheter will be introduced into the femoral vein, and visceral angiography will be performed to assess the arterial blood supply to the liver and to the lesion(s) identified on preprocedural imaging. All patients will undergo a distal super-selective catheterization of the hepatic arteries using a coaxial technique and microcatheters. Embolization will be performed with LC beads from BTG with a maximum size of 700 µm. The LC beads will be admixed with 8-15 mL of contrast and injected into the arterial branch at a rate of 1-2 mL/min. After embolization, angiography will be performed to determine the extent of vascular occlusion and to assess collateral tumor arterial supply. Patients will be observed carefully, and analgesia (morphine or meperidine) will be administered if necessary. Given the small tumor size included in this study, bilobar lesions will be treated sequentially during the same interventional procedure.

All operative MWAs will be performed in a laparoscopic or robot-assisted laparoscopic setting by one of four hepatobiliary surgeons with extensive experience with intraoperative US guidance and hepatic ablation ([name]). Care will be taken to create ample distance between the microwave near-field and any adjacent structures (diaphragm/heart, stomach/esophagus, colon, duodenum, gallbladder) by mobilization of the liver. All ablations will be guided by intraoperative ultrasound (BK Medical A/S, Herlev, Denmark) with care taken to allow for complete tumor treatment while preserving adequate distance between the microwave near-field and adjacent intrahepatic structures (portal pedicles, hepatic veins). Ablations will be performed with a 2.45-GHz generator with a 1.8-mm-diameter transcutaneous antenna (Acculis pMTA Accu2i; AngioDynamics Inc., Denmead, Hampshire, UK).

Operative variables will be recorded per patient, and individual ablation characteristics including tumor location by hepatic segment, proximity to a portal pedicle, number of applications, power settings, and ablation duration will be recorded for each individual tumor. A clearly demarcated zone of color flow Doppler activity will be visualized within 30 s of initiating the ablation to assure that the target is within the microwave ablation zone. Patients will be observed carefully, and analgesia will be administered per standard protocol if necessary.

Postprocedural Strategy

Division-specific standard guidelines will be applied to the postoperative care of patients included in this study. Postoperative complications will be recorded and treated symptomatically. All patients will be closely followed up for disease progression with clinical and laboratory examinations 4–6 weeks after ablation/TAE procedures, then every 3 months for the first 2 years. At 4–6 weeks following TAE +/- MWA procedures, tumors will be assessed radiographically and characteristics will be reported according to the LI-RADS criteria and guidelines. Imaging techniques will then be performed every 3 months during the first 2 years postoperative and every 6 months afterward. In addition, AFP levels will be obtained every 3 months during the first 2 years postoperative and every 6 months afterward.

Data Collection

All parameters will be prospectively collected. The study will be approved by the Internal Review Board of Carolinas Medical Center, and informed consent will be obtained from all patients prior to study participation. All hepatocellular carcinomas will be classified according to the TNM criteria of the American Joint Commission on Cancer (AJCC) 2010 Cancer System. A comprehensive medical history will be obtained from each patient and supplemented by clinical notes. Pre-, intra-, and postoperative variables (Table 1) and clinical outcomes will be recorded in an electronic database. Toxicity induced by TAE and or MWA will be graded according to the [Common Terminology Criteria for Adverse Events - CTCAE v5.0](#) (Slated for release in October 2015; v4.3 available at <http://evs.nci.nih.gov/ftp1/CTCAE/About.html>).

Table 1. Variables for analysis

Patient characteristics	age, sex, viral hepatitis status, nicotine use, alcohol use, drug use, hypertension, obesity, diabetes mellitus, general conditions, prior therapy, underlying disease status as determined by Child-Pugh and MELD score
Preoperative imaging	presence of cirrhosis; tumor size, location and number
Intraoperative findings	surgeon performing procedures, proximity of tumor to portal pedicle, number of TAE applications, number of MWA applications, power settings, ablation duration (per application and per tumor), pathology from random liver biopsy
Postoperative data	Tumor radiology, length of stay, 30- and 90-day readmission, wound infection, postoperative complications (encephalopathy, liver failure, ascites, upper GI bleeding), postoperative Δ MELD score
Tumor characteristics	BCLC classification, Okuda stage, AJCC clinical tumor stage, venous infiltration, lymphatic infiltration
Laboratory data	α -fetoprotein (AFP) level, Hb, leukocytes, thrombocytes, serum proteins, albumin, bilirubin, γ -GT, ASAT, creatinine, INR, alkaline phosphatase

Abbreviations: MELD, Model for End-Stage Liver Disease; TAE, transarterial chemoembolization; MWA, microwave ablation; GI, gastrointestinal; BCLC, Barcelona Clinic Liver Cancer; AJCC, American Joint Committee on Cancer; Hb, hemoglobin; γ -GT, gamma-glutamyl transpeptidase; ASAT, aspartate amino transferase; INR, international normalized ratio.

Definitions

Incomplete ablation is defined as enhancement present at the ablation border on arterial phase CT consistent with residual tumor on the initial post-ablation scan. Local recurrence is defined as an enhancing lesion contiguous with the ablation zone that is present on subsequent imaging but was not present on the initial postablation scan. Regional recurrence is defined as hepatic recurrence that is not adjacent to the ablation site. Metastatic recurrence is defined as extra-hepatic recurrence including lymph node metastases. Expected residual disease is defined as disease that was intentionally left

untreated at the initial MWA session. Further, liver-directed therapy is defined as any secondary hepatic ablation procedure for incomplete ablation or any recurrent disease. Survival will be calculated from the time of randomization until last recorded follow-up, liver transplantation, or death.

Intrahepatic disease-free survival time is defined as the time between randomization and absence of local or regional recurrence of HCC as determined by diagnostic imaging. Overall survival will be measured as time from randomization until last recorded follow-up, liver transplantation, or death from any cause. Perioperative mortality is defined as in-hospital mortality.

Quality of Life

Quality of Life (QOL) will be assessed prospectively in a subgroup of patients who undergo follow-up examinations in the outpatient clinic of our facility. The data will be collected for a maximum of 5 years postoperatively or until patient death. Regular follow-up checkups will be offered to patients at 2-, 3-, or 6-month intervals depending upon time elapsed from surgery, with frequency of checkups decreasing as postoperative period increases in duration.

Statistical Analysis

Patients alive at the time of analysis will be censored at the last follow-up examination or at liver transplantation. Univariate analyses will be performed using the log-rank test of equality for categorical variables and the chi-square test with Cox proportional hazard model for continuous variables to identify clinical variables (Child–Pugh class, Okuda class, Model for End-Stage Liver Disease (MELD) score, etiology of cirrhosis), tumor factors (extrahepatic disease, multicentric disease, tumor size, Milan criteria, AJCC tumor stage, AFP level), and treatment-related factors (TAE, complications, recurrence) predicting intrahepatic disease-free and overall survival. Survival and disease-free survival will be estimated using the Kaplan–Meier method and tested with the log-rank test following the intention-to-treat principle. Statistical analysis will be performed using SAS software (SAS Institute, Cary, NC, USA).

The analysis will be planned at a median follow-up of two years, with an interim analysis scheduled for 1 year after the first patient is enrolled or when 50% of total expected enrollment has been reached.

To improve patient selection in the future, additional exploratory analyses will be performed to identify potential prognostic factors. Table 1 details variables that will be included in a Cox proportional hazards regression model to obtain hazard ratios and 95% confidence intervals (CIs). All P values will be two-sided and a p value $< .05$ will be considered significant.

ETHICAL AND SAFETY CONSIDERATIONS

Protection of Patients

The techniques and procedures used in this study protocol are not investigational or provisional in nature; rather, they are established in the provision of care for patients of the HPB Division at Carolinas Medical Center. The therapeutic benefit of combination of TAE/MWA treatment in this patient population remains unknown and is the focus of this study. The additive risk for adverse events is expected to be equal to the individual risks of the study procedures in this protocol.

Standard Division-specific guidelines will be closely followed to ensure patient safety and clinical well-being during all procedures. Patients will be closely monitored for complications associated with MWA and TAE, including wound complications, hematologic toxicities, and others.

During the preparatory phase for procedures, the anesthesia personnel will evaluate the routine monitoring and support equipment. Several prophylactic actions may be employed to avert problems during the procedures. Adequate patient hydration prior to beginning the procedures will be ensured.

Protection of health care providers

Occupational health risks for health care providers include:

- Exposure to hepatitis, HIV, tuberculosis, or any infectious process;
- inadvertent inhalation of anesthetics;
- exposure to intraoperative X-rays; and
- Exposure to cytotoxic agents.

Strict adherence to Universal Precautions will be ensured at all times. Any blood, body fluid, or tissue from any patient will be considered potentially contaminated. Gloves, gowns, masks, and eye protection will be used to prevent contact between any contaminated object and the staff. The following items, which are not included under Universal Precautions, will be required:

- Use of unpowdered latex gloves.
- Use of the smoke evacuator to remove aerosols and vapors.
- Modifications to the routine operating room clean up.

- Recommended procedures for clean up of biohazardous or chemical spills.

[figure not shown]
Certain equipment will be available and appropriately utilized by personnel who come in contact with cytotoxic agents. This equipment will include: unpowdered latex gloves, impervious sterile gowns, protective eye wear, respirator mask (if a spill occurs), a spill kit, an impenetrable hazardous waste container, specially marked linen bags, and appropriate cytotoxic agent labels.

Protection of environment

Strict adherence to Universal Precautions will be maintained. Any biohazardous material will be separated from the standard trash and linen and placed in appropriate receptacles by the operating room staff. Biological waste will be stored onsite for 48 hours, then disposed of by a licensed hazardous waste facility. Bactericidal solutions will not be used to clean contaminated items; instead, 70% isopropyl alcohol will be used for clean up as recommended by the Occupational Safety and Health Administration (OSHA).

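### Secondary aim 1, feasibility of TAE + MWA, is to be judged from who enrolled, and no measure of whether the sequence was delivered is tied to it

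*Combined protocol and SAP*

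**What the plan says.** The Summary and the Objective section both state the aim as "to determine the clinical feasibility of TAE + MWA in HCC patients with a small tumor burden using patient demographics and disease characteristic data". The first secondary outcome, "Patient and disease characteristics (Table 1", points to Table 1 under Data Collection.

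Other items bear on delivery or tolerability:

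- Outcomes in the Objective section: a count of embolizations, "Number of TAE procedures required (for multilobar lesions or repeat effect"; graded adverse events, "Toxicity induced by TAE and or MWA using the latest published full version of Common Terminology Criteria for Adverse Events"; and surgical morbidity, "1-month and 3-month postoperative morbidity using the Clavien-Dindo Classification of Surgical Complications".
- The intraoperative row of Table 1: "number of TAE applications, number of MWA applications, power settings, ablation duration (per application and per tumor". Its postoperative row adds complications and readmissions.
- The Definitions section defines incomplete ablation but does not list it as an outcome.
- A CONSORT flow diagram is named as Figure 1; its content is not visible in the text available.

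The sequence is set out under Patient Eligibility and Allocation and again under Procedural Strategy: "TAE treatments will be initiated within one week of randomization, then followed by MWA within 4 to 6 weeks after reviewing radiological scans from TAE". Procedural Strategy also states: "After embolization, angiography will be performed to determine the extent of vascular occlusion and to assess collateral tumor arterial supply".

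Statistical Analysis covers Kaplan-Meier estimates and log-rank tests by intention to treat, univariate analyses of prognostic factors, and a Cox model that takes the Table 1 variables as covariates. It does not mention feasibility.

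**The concern.** Feasibility of a staged treatment means that patients assigned to it can receive the first step, go on to the second, and tolerate both. Age, hepatitis status, tumor size and BCLC stage cannot show this. They are mostly fixed before treatment, and randomisation tends to balance them between arms.

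The Background gives feasibility as one reason why randomised trials are needed and says that the best protocol and timing for the combination are unsettled. If the aim is analysed as worded, the report will contain a description of the patients and no estimate of how often the combination was delivered. Any delivery figure added later would have a denominator chosen after the data were seen.

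**Working it through.** **No figure to reproduce.** The documents state no completion rate, success threshold or target precision for feasibility. The check is therefore whether any planned item supplies a measure, a denominator and an analysis.

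**Items side by side.**

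- *Demographics and disease characteristics* (the measure named in the aim): describe patients; give no delivery result.
- *Number of TAE procedures; TAE and MWA applications*: if recorded for every randomised patient, a zero would identify someone who missed a step. The plan states neither that denominator nor a proportion.
- *CTCAE toxicity, Clavien-Dindo morbidity*: bear on tolerability, not on the share of patients who received both steps.
- *Incomplete ablation*: a technical result, defined but not tied to the aim.
- *CONSORT diagram*: may show flow; not tied to the aim, and no interval estimate is planned.
- *Procedure dates, TAE-to-MWA interval, occlusion result, reasons for non-completion*: not listed in Table 1 or among the outcomes.
- *Statistical Analysis*: uses Table 1 only for prognostic modelling.

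No item supplies all three.

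**Why the denominator must be stated.** Suppose 40 of 50 patients randomised to the combination receive both steps. Over all randomised the result is 40/50 = 80%. Over those who completed treatment it is 40/40 = 100%. The plan does not say which would be reported.

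**Residual disease.** The exclusion list under Patient Eligibility and Allocation includes residual disease at the first CT after MWA, which can be known only after treatment. These patients have had MWA, so removing them would not raise a delivery proportion. It would, however, make the denominator depend on outcome and drop technical failures that belong beside the estimate.

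**Timing.** The four-to-six-week interval before MWA in the combination arm can be counted from TAE or from review of the post-TAE scans. Postprocedural Strategy puts radiographic assessment at 4–6 weeks after the procedures. If that is the scan meant (an assumption), counting from its review places MWA at 4 + 4 = 8 to 6 + 6 = 12 weeks after TAE, against 4 to 6 weeks if counted from TAE. A patient ablated 10 weeks after TAE meets one reading and fails the other.

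**Precision at the planned size.** Sample Size gives 50 patients per arm. The completion counts below are assumptions. The exact (Clopper-Pearson) limits for x of n are:

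lower = Beta quantile 0.025 with parameters (x, n − x + 1)
upper = Beta quantile 0.975 with parameters (x + 1, n − x)

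- 40/50 = 80%: Beta(40, 11) and Beta(41, 10) give 66.3% to 90.0%
- 45/50 = 90%: Beta(45, 6) and Beta(46, 5) give 78.2% to 96.7%
- 48/50 = 96%: Beta(48, 3) and Beta(49, 2) give 86.3% to 99.5%

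Half-widths run from (99.5 − 86.3)/2 = 6.6 to (90.0 − 66.3)/2 ≈ 11.9 percentage points. Under the 2:1 option (83 patients, so about 83 × 2/3 ≈ 55 in the combination arm), 50/55 gives 80.0% to 97.0%.

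**The case against.** The strongest reply is that the plan already holds much of what is needed. Table 1 is not purely baseline, several safety outcomes bear on clinical feasibility, survival is compared by intention to treat, and a flow diagram is foreseen. All of this is true. A reader might infer that the plan records nothing relevant, or that patients who miss a step vanish from the trial; the documents support neither. What they lack is a link from these items to the aim, and a stated proportion, denominator and analysis.

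The opposite inference, that the required data are all collected and only wording must change, is not supported either. Dates, occlusion result and reasons for non-completion arise in care, but the plan does not list them as trial variables.

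A reader might also take the 5–10% withdrawal allowance under Sample Size as a forecast of failed embolization. It covers both arms, and its examples are disease found at operation to be more advanced. Appendix VI lists contraindications to the beads as product information, not as a prediction for this trial.

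Finally, the aim may mean finding in which patients the combination is feasible. That is a fair reading, and it would explain the mention of characteristics. It still needs a per-patient record of whether the sequence was delivered, to which those characteristics can be related.

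**Conclusion.** The point holds. The measure named for secondary aim 1 does not answer it, and nothing elsewhere in the plan supplies a feasibility estimate. The defect lies in how the aim is measured and analysed, not in a complete absence of relevant data.

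The planned arm is large enough for a useful descriptive estimate, to within about 7 to 12 percentage points if true completion lies between 80% and 96%. That range is assumed. It is not large enough to separate, say, 80% from 90% with confidence, since the two intervals overlap widely.

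This should be changed, but it concerns a secondary aim; the primary analysis is unaffected.

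**What to change.** 1. Replace the measure in aim 1 with the proportion of all patients randomised to MWA + TAE who received TAE and then MWA, with an exact 95% confidence interval. Tabulate reasons for non-completion at each step, and report the proportion reaching MWA in the control arm alongside.
2. Keep demographics and disease characteristics to describe who did and did not complete.
3. Report adherence to the protocol's timing separately, after the sponsor reconciles Patient Eligibility and Allocation, Procedural Strategy and Postprocedural Strategy on the event from which the 4 to 6 weeks is counted.
4. Report angiographic occlusion descriptively, not as part of a composite, because the documents give no threshold for it.
5. Report toxicity and morbidity alongside as tolerability.
6. State that patients with residual disease at the first CT after MWA stay in the feasibility denominator.

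The cost is protocol and SAP wording plus a few form fields: procedure dates, occlusion result and reason for non-completion. No procedure is added. The feasibility figure may look less favourable, because every randomised patient counts.
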